**Endpoints:**

Primary Endpoint: Composite count of ED visits and hospitalizations during 3 months of intervention and 15 months of follow up (18 months observation).

Due to the covid pandemic and recommendations from the DSMB, after 4/30 all participants' post-activity period follow up will be limited to 9 months (12 months of observation), or truncated to the current observation period total of between 12 and 18 months.

Secondary Endpoints:

- 1) Dialysis treatment adherence – mean missed minutes per month
- 2) Mean monthly inter-dialytic weight gain (%), serum albumin (g/dL);
- 3) Perceived self-efficacy, knowledge, perception of social support and quality of life.

Feasibility Endpoints (intervention only):

- 1) number of telephone contacts per week;
- 2) content of telephone conversations;

Feasibility of Peer Mentor Training:

- 1) attendance records for all sessions
- 2) change in pre-/post-knowledge assessments after training
- 3) content & descriptive evaluation of course evaluations

Peer mentorship to improve outcomes in patients on maintenance hemodialysis (PEER-HD) Version 3.0  
Protocol 2018-01  
30 April 2021

**Study Population:** 20 Mentor adult in-center hemodialysis patient participants  
200 Adult in-center hemodialysis patient participants  
Enrolled from dialysis units in or near the Bronx, NY and Nashville, TN

**Trial Type:** Pragmatic Randomized Trial

**Description of Sites/Facilities Enrolling Participants:** Participants are enrolled from multiple dialysis units affiliated with Albert Einstein (AECOM) College of Medicine and Vanderbilt University Medical Center (VUMC). AECOM will serve as the coordinating center.

**Description of Study Intervention:** Intervention will have 2 phases:  
1) **Mentor training**

- 4 Training sessions, 2 hours each covering topics in dialysis care, coaching and motivational interviewing techniques.
- Refresher 2-hour session at 3-months and 10-months
- Financial compensation by hour for training
- Assessments of skills, role modeling & simulations, exit interviews

2) **Telephone based 3-month intervention** by mentors for mentees

- Weekly phone contact with mentee (1-3 mentees per mentor)
- Social mixers at the dialysis facility, or other group activities

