### 1.2 SCHEMA

**Figure 1. Mentors N~20**

**Figure 2. Patient Participants N=200 [All sites; Estimated enrollment AECOM=140; VUMC=60]**

At the final study visit, all mentors and those randomized to the peer mentoring intervention will complete program evaluation interviews and surveys to gain feedback on the intervention.

Due to impact of the covid pandemic, the study DSMB recommended prioritizing enrollment and reduction of follow-up observational time. The recommendation is to limit total observation time to 12-months for intervention and control participants. Participants currently enrolled and who have passed the 12-month point will execute their T2 visit as soon as possible and truncate observation (13-18 months). For those whose observation time is less than 12-months, or any new enrolled participants, the T2 assessment will be moved to the 12-month time point. Mentors, may complete T2 at 18-months (Einstein site), or may complete T2 visit at 12-months if all other mentor activities have been completed at the site. Medical record monthly review will only occur for the observation period and will also be truncated at the time of the T2 visit. This alteration of the study design was approved by the DSMB and also the NIH program officer.

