## 9.2 SAMPLE SIZE DETERMINATION

For evaluation of the primary endpoint, estimates are based on local dialysis unit hospitalization events in the past 12 months. For the control group, we expect 0.27 events per month (100 prevalent patients and 27 composite events per month). With 73 patients per group (after 25% drop-out), our study has >80% power to detect 20% reduction (i.e. a reduction of 0.054 visits per person-month) at type 1 error level 0.05. We will recruit at least 100 patients per group over the course of the study.

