## 9.3 POPULATIONS FOR ANALYSES

For the primary endpoint comparison, an intention-to-treat analysis will be used, including all available data on randomized participants. It is expected that up to 20% of randomized participants may discontinue from the study prior to the end point. These participants will be included in the primary analysis and data from the monthly outcome ascertainment up until the last available time point will be used. As preparation for the follow-up period modification, events to date were evaluated at one site (Einstein) and were found to be more frequent than initial estimates. This informed the request for reduction in the follow-up period.

The characteristics of those who do not complete all study activities will be compared to those with complete follow-up to examine for potential biases introduced by differential follow-up among the two groups. These will be considered ancillary analyses.

Secondary analyses will examine additionally an as-treated population. This will group any intervention patient who did not participate in more than 20 minutes total of the intervention during the three-month period to be classified as the usual care group.

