#### 9.4.2 ANALYSIS OF THE PRIMARY ENDPOINT(S)

##### ED Visit and Hospitalization Count

Each month all enrolled patients will be evaluated for ED visit or hospitalization encounters by both self-report and medical record review. The events will be tabulated each month up to an 18-month period of follow-up. The rates of the composite event will be determined as event per patient-month and compared between the intervention and usual care group using Poisson regression with two random intercepts. In the regression model, the composite counts of ED visits and hospitalization during up to 18-months follow-up is the outcome variable and the intervention assignment of the mentees is the primary binary predictor. The log of follow-up time will be included as offset. The random intercepts will account for the correlation between mentees who share a common mentor as well as the correlation between mentees who are from a common dialysis facility (out of seven facilities). As a randomized controlled trial, we do not anticipate the need for covariate adjustment. However, if evaluation of patient characteristics by group identifies a failure of randomization and imbalance in key characteristics as an example including age, gender, comorbidity, race, or dialysis vintage they will be considered as adjustment variables in the analysis. We will control for type 1 error at 0.05. An exploratory analysis will consider the comparison between the groups but at 3-months of observation after the conclusion of the intervention delivery.

We will perform residual analysis for the mixed effects models. For mixed effects models, we will examine marginal residuals to check linearity and within-subjects covariance matrix and conditional residuals to check outliers as well as normality and homoscedasticity of the residual errors. In case Pearson residual analyses indicate overdispersion in the Poisson mixed effects model, we will perform quasi-Poisson model. We will use robust sandwich estimator in the presence of misspecification of the covariance matrix (i.e. random effects structure).

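### The power claim above 80% in section 9.2 matches the old 18-month follow-up; at the 12-month cap, on the stated event rate, power is about 63–76%

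*Combined protocol and SAP*

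**What the plan says.** Section 9.2 plans on a control rate of 0.27 composite events per person-month, a 20% reduction and a type 1 error of 0.05: "With 73 patients per group (after 25% drop-out), our study has >80% power to detect 20% reduction". At least 100 per group are to be recruited. The section states no observation period and makes no allowance for extra-Poisson variation or clustering. Section 9.4.1 makes all tests two-sided.

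The synopsis gives the original primary endpoint as an 18-month count, then amends it: after 30 April, "post-activity period follow up will be limited to 9 months (12 months of observation), or truncated to the current observation period total". The synopsis puts that truncated total at 12 to 18 months. The schema (section 1.2) adds, for participants "whose observation time is less than 12-months, or any new enrolled participants, the T2 assessment will be moved to the 12-month time point".

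Section 9.3 puts losses at a different level from 9.2: "It is expected that up to 20% of randomized participants may discontinue from the study prior to the end point". It keeps their partial data: "data from the monthly outcome ascertainment up until the last available time point will be used". It also gives a reason for the shorter follow-up: "events to date were evaluated at one site (Einstein) and were found to be more frequent than initial estimates". No observed rate or revised power follows.

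Section 9.4.2 specifies a Poisson model with random intercepts for mentor and facility. On exposure it says "The log of follow-up time will be included as offset", and on extra variation "In case Pearson residual analyses indicate overdispersion in the Poisson mixed effects model, we will perform quasi-Poisson model".

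**The concern.** For a count endpoint analysed as a rate, information is driven by events, and so by person-time multiplied by rate. Cutting observation from 18 to 12 months removes up to a third of the expected events. A power statement with no follow-up time cannot show whether it belongs to the old design or the new one, and the rate, sample size and power printed in 9.2 carry no adjustment for the cut.

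What is at stake is how a null primary result is read. If it is set against power above 80% when the trial had about 70%, the absence of a 20% reduction will look better established than it is.

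**Working it through.** **Inputs.** Control rate 0.27 per person-month, rate ratio 0.80 (so 0.216), 73 analysed and 100 recruited per group (9.2); two-sided 0.05 (9.4.1); 1:1 allocation (4.1); 18 months originally, now 12, or 12–18 for those already past month 12 (1.1, 1.2).

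**Formula.** With n per group and T mean months per person, for independent Poisson counts:

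SE = √[1/(n·0.27·T) + 1/(n·0.216·T)], z = |ln 0.8|/SE, power = Φ(z − 1.96).

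**Reproducing the plan's figure.** With n = 73 and T = 18, z = 2.802 and power is 80.0%; with n = 72 it is 79.5%. Solving for n at 80% power:

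| Method | 18 months | 12 months |
|---|---|---|
| Log rate | 72.98 | 109.5 |
| Square root | 72.4 | 108.7 |
| Rate difference | 72.7 | 109.0 |

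All three round up to 73 at 18 months, and 73/0.75 = 97.3 is consistent with recruiting 100. The 18-month basis is inferred from this match.

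**Person-time needed.** 80% power needs 73 × 18 ≈ 1,314 person-months per arm. With 100 per arm that is 13.1 months per randomised person. A 12-month cap supplies at most 100 × 12 = 1,200, so full retention would not close the gap on the stated rate.

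**Power on the stated rate.** Section 9.3 keeps partial data, so leavers contribute time until they leave. The timing of leaving is assumed.

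| Scenario | T (months) | Power |
|---|---|---|
| 73 per group, 12 months | 12 | 62.9% |
| 100 per group, no loss | 12 | 76.4% |
| 100, 20% leave at month 3 | 0.8×12 + 0.2×3 = 10.2 | 69.4% |
| 100, 20% leave at month 6 | 10.8 | 71.9% |
| 100, 20% leave at month 9 | 11.4 | 74.2% |
| 100, 25% leave at month 6 | 0.75×12 + 0.25×6 = 10.5 | 70.7% |
| Old design: 100, 20% leave at month 9 of 18 | 0.8×18 + 0.2×9 = 16.2 | 87.5% |

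Like for like (100 per group, 20% leaving halfway), the cut takes power from 87.5% to 71.9%. In simulated Poisson data (40,000 runs), power was 0.802 (73 × 18), 0.626 (73 × 12), 0.723 (100, 20% halfway) and 0.766 (100 × 12).

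**Credit for longer-followed participants.** Suppose 20% leave at month 6 and a fraction f of completers have the full 18 months. Then T = 1.2 + 0.8(12 + 6f). With f = 25%, T = 12.0 and power is 76.4%; with f = 50%, T = 13.2 and power is 80.2%. Reaching 80% needs f of about 49%, or about 59% if drop-out is 25%. The documents do not give f.

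**What would restore 80% at 12 months.** The required control rate is 0.27 × 1,314 divided by the person-months available. The last column keeps the rate at 0.27.

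| Scenario | Person-months | Rate needed | Reduction detectable at 0.27 |
|---|---|---|---|
| 100, no loss | 1,200 | 0.296 | 21% |
| 100, 20% halfway | 1,080 | 0.328 | 22% |
| 73 | 876 | 0.405 | 24% |

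**Overdispersion.** The documents give no value. Multiplying the variance by an assumed 1.25, 1.5 or 2 gives:

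| Scenario | 1.25 | 1.5 | 2 |
|---|---|---|---|
| 73 per group, 18 months | 71% | 63% | 51% |
| 73 per group, 12 months | 53% | 46% | 37% |
| 100 per group, 12 months, no loss | 67% | 59% | 47% |

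**The case against.** The strongest reply is that 0.27 is probably too low. Section 9.3 says events at Einstein ran ahead of plan, and the schema expects 140 of the 200 participants there. The planning rate came from prevalent patients in local units, whereas section 5.1 requires at least one risk criterion, such as a recent hospitalisation or ED visit, or a catheter. A pooled rate about 10% above plan (0.296) restores 80% with 100 per group and no loss; about 21–22% above (0.328) does so with 20% leaving halfway. This stands as a reason why actual power may be adequate. It does not rescue the printed claim, because no rate is given, the review covered one site, and 9.2 still rests on 0.27.

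A second reply is that 63% is too harsh: 73 × 12 gives leavers no person-time and gives nobody more than 12 months. That is fair as a description of the analysis in force. The figure is kept because 73 is the number 9.2 itself uses; the partial-data scenarios at 69–74% are the more realistic 12-month figures.

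Third, the DSMB and the NIH program officer approved the change, so power may have been reconsidered elsewhere. That is possible. What can be said is that no revised calculation appears in the documents.

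Finally, the effect is modest. With 100 per group the detectable reduction moves only to 21–22%, the analysis stays valid, and confidence intervals will be reported. Planning on 25% drop-out while expecting up to 20% is also a conservative choice. These points limit the severity but leave the stated power unsupported.

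**Conclusion.** The concern holds. The stated power is reproduced by the superseded 18-month design with no margin, and does not carry over to the 12-month cap on the plan's own rate. There it is about 63% (73 per group) to 76% (100 per group, no loss), and 69–74% with partial data kept and 20% leaving.

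These figures rest on independent Poisson counts, a rate of 0.27, a 20% reduction and two-sided 0.05, with assumed timing of losses. A higher event rate, or about half of completers reaching 18 months, would bring power back to 80%; overdispersion and mentor correlation would lower it. The documents fix none of these, so actual power cannot be determined. The primary analysis itself is not invalidated. This should be fixed because it misstates the design's sensitivity.

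**What to change.** Restate section 9.2 for the design in force:

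- Give the observation period and the actual distribution of follow-up, including how many participants have between 12 and 18 months.
- Report the pooled event rate and variance (not by arm) from the site review, and extend the review to the second site if its data are available.
- Use one drop-out figure in 9.2 and 9.3, and say how partial follow-up enters the calculation.
- Show power over a stated range of overdispersion and mentor clustering.
- Replace the claim of more than 80% with the resulting power range and detectable reduction. On 0.27 per month at 12 months, before those allowances, these are about 63–76% and 21–24%. If the observed pooled rate restores 80%, state that rate and show the calculation.

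The cost is a wording amendment with its usual IRB approval, plus a blinded summary of rate, variance and follow-up. The site review already supplies part of this. No extra patients or change to the analysis is needed. The downside is a less favourable stated power.

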## 2.2 BACKGROUND

### 2.2.1. Excessive hospitalization rates in patients treated with hemodialysis

There are over 400,000 ESKD patients in the United States and they constitute one of the most clinically complex and expensive patient groups. Patients treated with hemodialysis comprise 1% of the Medicare population but account for close to 9% of the total expenditures. Hospitalizations drive up to 40% of the cost for ESKD care. Patients receiving hemodialysis are hospitalized, on average, 2 times per year and over 35% of these patients are re-hospitalized within 30 days of discharge. During hospitalizations, patients' nutritional status and mobility deteriorate, and the risk for infectious complications increases, all of which add to short-term morbidity and mortality.

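### The >80% power claimed for 73 per group carries no allowance for overdispersion, which the protocol's own background and analysis plan make likely

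*Combined protocol and SAP*

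**What the plan says.** Section 9.2 sets the control rate from local unit records: "For the control group, we expect 0.27 events per month (100 prevalent patients and 27 composite events per month". It continues "With 73 patients per group (after 25% drop-out" and claims that "our study has >80% power to detect 20% reduction (i.e. a reduction of 0.054 visits per person-month", "at type 1 error level 0.05". It adds: "We will recruit at least 100 patients per group over the course of the study". No standard deviation, dispersion factor, intraclass correlation or follow-up length appears there. Section 9.4.1 makes tests two-sided.

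Section 2.2.1 says that hemodialysis patients are "hospitalized, on average, 2 times per year and over 35% of these patients are re-hospitalized within 30 days of discharge". Section 2.2.2 gives 38% for 30-day re-hospitalization after fluid-overload admissions.

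The primary model in Section 9.4.2 is a Poisson regression with mentor and facility random intercepts and a follow-up-time offset. It has no patient-level term. For extra variation it says: "In case Pearson residual analyses indicate overdispersion in the Poisson mixed effects model, we will perform quasi-Poisson model".

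**The concern.** A power calculation for counts needs a variance as well as a mean. Section 9.2 gives only the mean, and its sample size matches the smallest variance usually assumed for counts, where variance equals mean. Repeat admissions that concentrate in some patients, or come in bursts, make the variance larger. The quasi-Poisson fallback would then widen the standard error by a factor that the sample size did not allow for.

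The interpretation of the result is at stake. A null finding from a trial described as having more than 80% power would be read as evidence against a 20% reduction, when the chance of detecting one may have been materially lower.

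**Working it through.** **Inputs.** From Section 9.2: 0.27 events per patient-month, rate ratio 0.80 (0.27 to 0.216), 73 per group, alpha 0.05. From Section 9.4.1: two-sided tests. The 18 months is the full observation period in the Section 1.1 synopsis before truncation. It is used throughout, unless stated, to keep this point separate from the shortened follow-up.

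**1. Reproduce the plan's figure.** Expected counts are m0 = 0.27 × 18 = 4.86 and m1 = 0.216 × 18 = 3.888, so 1/m0 + 1/m1 = 0.2058 + 0.2572 = 0.4630. With variance equal to mean and a Wald test on the log rate ratio:

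n = (1.960 + 0.842)² × 0.4630 / (ln 0.8)² = 7.849 × 0.4630 / 0.04979 = 72.98, so 73.

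At n = 73, SE = √(0.4630/73) = 0.0796 and power = Φ(0.2231/0.0796 − 1.960) = 80.0%. Rate-difference and square-root versions give 72.67 and 72.45, also 73. On the log scale, two-sided tests at 15 and 12 months need 88 and 110; one-sided tests at 12, 15 and 18 months need 87, 69 and 58. Only the two-sided 18-month case returns 73.

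**2. Compare a Poisson process with the protocol's background.** At 2 per year the expected count in 30 days is 2 × 30/365.25 = 0.1643, so the chance of another event is 1 − exp(−0.1643) = 15.1%. At 0.27 per month it is 1 − exp(−0.2661) = 23.4%. Reaching 35% needs −ln(0.65) × 365.25/30 = 5.2 events per year.

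**3. Short-term clustering (variance = φ × mean).** The SE is multiplied by √φ, so power = Φ(0.2231/√(φ × 0.4630/n) − 1.960).

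| φ | 73 per group | 100 per group, all followed 18 months |
|---|---|---|
| 1.0 | 80% | 91% |
| 1.1 | 76% | 88% |
| 1.33 | 68% | 81% |
| 1.53 | 62% | 76% |
| 1.9 | 53% | 66% |

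The values 1.33 and 1.53 assume that all of the excess 30-day risk is short-term: φ = 1 + 2e, with e = −ln(0.65) minus the expected 30-day count. This gives 1 + 2(0.4308 − 0.2661) = 1.33 at 0.27 per month and 1 + 2(0.4308 − 0.1643) = 1.53 at 2 per year. A simulated self-exciting process matched to 35% gave about 1.56 and 1.9 for the same two rates.

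**4. Persistent patient differences (variance = mean + k × mean²).** SE² = (0.4630 + 2k)/n. A small k of 0.10 gives SE = √(0.6630/73) = 0.0953 and 65% power. If the whole 35% came from gamma frailty, 1 − (1 + kλ)^−(1/k + 1) = 0.35, with λ the expected 30-day count, gives k = 0.78 at 0.27 per month and 2.04 at 2 per year. Power is then about 27% and 14%.

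**5. What could offset the loss.**
- Recruiting 100: if all were followed for 18 months, 80% power needs φ of at most 100/72.98 = 1.37.
- Partial data: if 25% leave halfway on average (an assumption), the information equals 75 + 12.5 = 87.5 patients per group. Power is then 87% at φ = 1, 76% at 1.33 and 70% at 1.53.
- A higher event rate under short-term clustering: at twice the rate with φ = 1.7, 73 per group has 86% power (70% at 12 months). At an assumed 0.35 per month, φ = 1 + 2(0.4308 − 0.3450) = 1.17 and power is 84%.
- A higher event rate under persistent differences: as counts rise, SE² falls only to 2k/n. So 80% power at any rate needs k of at most n × 0.04979/(2 × 7.849), which is 0.23 at 73 per group and 0.32 at 100.

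**The case against.** The arithmetic in Section 9.2 reproduces; what is questioned is an assumption that it does not state. The background figures are cited hospitalization data for hemodialysis patients generally, while the 0.27 is a local count of ED visits and hospitalizations together. The denominator of the 35% is also unclear. If it means patients with any 30-day readmission in a year, simulated Poisson events give 23% of all patients (27% of those hospitalized) at 2 per year, still short of 35%. At the composite rate of 3.24 per year they give 47%, and the conflict disappears. That last comparison sets a hospitalization figure against a rate that includes ED visits. The 0.27-per-month calculations above mix measures in the same way.

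Section 9.3 keeps dropouts' data up to their last time point, and at least 100 per group are recruited, so 73 complete patients understates the information. Section 9.3 also reports more events than expected at one site. Section 9.4.2 guards type I error with quasi-Poisson and a sandwich estimator.

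Much of this stands. A reader might infer that the background figures rule out Poisson counts for the composite; they do not, for the reasons just given. A reader might also infer that the higher event rate cannot help; that holds only under persistent patient differences, and no rate is reported. What the objection does not remove is that Section 9.2 attaches its claim to 73 per group, where there is no margin. Quasi-Poisson protects type I error by widening the standard error, and that widening is the loss of power in question.

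**Conclusion.** The unqualified power claim is not supported. At 73 per group, 0.27 per month and 18 months, any variance above the mean takes power below 80%. The protocol's readmission figures and its quasi-Poisson fallback make some excess the expected case. The direction is firm, given the inferred Poisson basis.

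The size is not firm. Power of 53% to 68% is illustrative of short-term clustering with variance-to-mean ratios from 1.9 down to 1.33, and it assumes that the hospitalization figures carry over to the composite in enrolled patients. The 27% and 14% figures are an upper-bound scenario for the loss, with every excess readmission assigned to permanent patient differences under one gamma model. They should not be quoted as the trial's power. Nor do the documents support saying that a true 20% reduction would more likely than not be missed: at 68% power about one in three would be. With 100 per group fully followed for 18 months, the mildest case (1.33) still reaches 81%.

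The shorter follow-up is a separate matter: 73 per group at 12 months has 63% power even with no overdispersion. Correlation by mentor and facility is also missing from Section 9.2 and is not included here.

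**What to change.** In Section 9.2, replace variance equal to mean with an overdispersed variance (φ × mean, or negative binomial). Estimate it from the trial's own monthly patient-level counts pooled across arms, or from the local unit records if they hold counts per patient; Section 9.2 shows only an aggregate. Pooling needs no comparison between arms. It overstates dispersion slightly if there is an effect: rates of 0.27 and 0.216 have mean 0.243 and SD 0.027, adding (0.027/0.243)² = 0.012 to k.

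Then restate the power for a 20% reduction, or the reduction detectable with 80% power, as a range over plausible dispersion at the enrolled size and actual follow-up. Remove the unqualified >80% claim.

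The cost is one recalculation and revised wording, with a less favourable stated power as the downside. No extra patients, visits or data collection are needed.
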